## 13. STATISTICS

In addition to this section of the study protocol, a Statistical Analysis Plan (SAP) will be developed and finalized prior to the final database lock and unblinded data analysis. The SAP will provide a detailed description for the handling of missing data, subject eligibility criteria for the analysis, and statistical methodology for the data summary and between-group comparisons.

Statistical analysis will be done by the Sponsor or under the authority of the Sponsor. A general description of the statistical methods to be used to analyze the safety and efficacy data is outlined below. Specific details will be provided in the SAP.

Additional sensitivity analyses may be performed due to the COVID-19 pandemic. All analyses related to COVID-19 will be conducted in accordance with regulatory guidelines. These analyses will be described in the SAP.

### 13.1. Study Endpoints

#### 13.1.1. Primary Endpoint

##### 13.1.1.1. Safety

- Incidence of TEAEs and treatment-emergent SAEs
- Proportion of subjects discontinuing study treatment due to TEAEs

#### 13.1.2. Secondary Endpoint

##### 13.1.2.1. Biological Activity

- Rate of decline in FVC over 24 weeks (measured in mL and % of predicted over unit time)
- Absolute and relative change in FVC (mL and % of predicted) at Visit 14 (Day 169) as compared with baseline
- Proportion of subjects with an FVC response (mL and % of predicted) defined as either having improvement or a decline by 0% to  $\leq 5\%$ ,  $> 5\%$  to  $\leq 10\%$ , and by  $> 10\%$  at Visit 14 (Day 169)
- Change in DLCO and DLCO corrected for hemoglobin
- Changes of ILA as measured by HRCT (ie, change in parenchymal feature [Baseline to Visit 14 (Day 169)]), as determined by qualitative assessment (central radiologist) and quantitative analysis (Quantitative Lung Fibrosis – QLF analysis)
- Time to first acute IPF exacerbation (ie, an unexplained worsening of dyspnea, evidence of hypoxemia as defined by worsened or severely impaired gas exchange, new radiographic alveolar infiltrates, and an absence of an alternative explanation such as infection, pulmonary embolism, pneumothorax, or heart failure [Raghu et al, 2011])

- Rate of hospitalization for respiratory ailments, rate of mortality due to all causes, and rate of deterioration of IPF resulting in lung transplantation (up to 12 weeks after the end of study treatment) or death

## 13.2. Statistical Plan

### 13.2.1. Populations of Interest

Safety Population: The safety population will include all subjects who receive at least 1 dose of study treatment.

ITT Population: The intent-to-treat (ITT) population will include any randomized subjects.

PK Population 1: This PK population will include subjects in the PK subset who receive at least 1 dose of study treatment and have a majority of scheduled PK samples drawn for serial PK measurements that allow for PK parameters to be generated. Subjects who do not complete the study treatment infusion (Visit 2) will be excluded from PK analysis.

PK Population 2: This PK population will include subjects who receive the majority of the study treatment doses and also have a majority of the planned trough samples collected that allow for a comparison of trough levels across dosing weeks.

Per Protocol: This population will exclude nonevaluable subjects and subjects with major protocol deviations thought to impact the ability to assess the effect of study treatment.

Exclusion of subjects from the Per Protocol (PP) set will be reviewed, documented, and approved before the study is unblinded to the study Sponsor. The criteria for excluding subjects from the PP population will be specified in the SAP.

### 13.2.2. Demographic and Baseline Characteristics

The safety population will be used for summary of demographic and baseline characteristics.

Demographic and baseline laboratory results will be summarized overall and by treatment arm using descriptive statistics. Additionally, the proportion of subjects on SOC upon randomization for each treatment arm will be summarized.

### **13.2.3. Safety**

All safety analyses will be performed on the safety population.

The analysis of safety, reported for each treatment arm, will be based on the frequency of AEs and their severity for all treated subjects. The safety variables, including AEs, SAEs, and AEs of interest (coded using the Medical Dictionary for Regulatory Activities [MedDRA]), clinical laboratory tests [REDACTED] physical examination, ECGs, and vital signs will be summarized or tabulated by treatment arm. Some of the variables will be tabulated by treatment arm and by visit. Incidence of AEs will be further tabulated by subjects on SOC within each treatment arm.

The proportion of subjects discontinuing study treatment due to AEs will be tabulated by treatment arm.

### 13.2.5. Pharmacokinetics

A black and white image showing a series of horizontal bars of increasing length from left to right, suggesting a step function or a series of steps. The bars are black on a white background, and the lengths of the bars increase progressively from left to right.

A horizontal bar chart showing the distribution of data across 12 categories. The bars are black with white outlines. The first category has a small bar. The second category has a large bar. The third category has a small bar. The fourth category has a large bar. The fifth category has a small bar. The sixth category has a large bar. The seventh category has a small bar. The eighth category has a large bar. The ninth category has a small bar. The tenth category has a large bar. The eleventh category has a small bar. The twelfth category has a large bar.

### 13.3. Determination of Sample Size

Approximately 120 subjects will be enrolled into the study, with approximately 40 subjects in each of 3 arms. The study will include approximately 35-40 sites and will enroll approximately 3 to 5 subjects per site.

### 13.4. Deviation from Original Analysis Plan

All deviations from the original SAP will be provided in the final clinical study report.

## **14. ADVERSE EVENTS**

### **14.1. Adverse Event Definitions**

#### **14.1.1. Adverse Event**

An AE means any untoward medical occurrence associated with the use of a drug in humans, whether or not considered drug-related. An AE (also referred to as an adverse experience) can be any unfavorable and unintended sign (eg, an abnormal laboratory finding), symptom, or disease temporally associated with the use of a drug and does not imply any judgment about causality. An AE can arise with any use of the drug (eg, off-label use, use in combination with another drug) and with any route of administration, formulation, or dose, including an overdose.

#### **14.1.2. Suspected Adverse Reaction**

Any AE for which there is a reasonable possibility that the drug caused the AE. For the purposes of Investigational New Drug (IND) safety reporting, “reasonable possibility” means there is evidence to suggest a causal relationship between the drug and the AE. Suspected adverse reaction implies a lesser degree of certainty about causality than adverse reaction, which means any AE caused by a drug.

#### **14.1.3. Life-Threatening Adverse Event or Life-Threatening Suspected Adverse Reaction**

An AE or suspected adverse reaction is considered “life-threatening” if, in the view of either the Investigator or Sponsor, its occurrence places the subject at immediate risk of death. It does not include an AE or suspected adverse reaction that, had it occurred in a more severe form, might have caused death.

#### **14.1.4. Serious Adverse Event or Serious Suspected Adverse Reaction**

An AE or suspected adverse reaction is considered “serious” if, in the view of either the Investigator or Sponsor, it results in any of the following outcomes:

- Death
- A life-threatening AE – see definition above
- Admission to the hospital or prolongation of existing hospitalization
- A persistent or significant incapacity or substantial disruption of the ability to conduct normal life functions
- A congenital anomaly/birth defect

Important medical events that may not result in death, be life-threatening, or require hospitalization may be considered serious when, based upon appropriate medical judgment, they may jeopardize the subject and may require medical or surgical intervention to prevent one of the outcomes listed in this definition. Examples of such medical events include allergic

---

 Admission to the hospital for a scheduled PK blood sample collection will not be considered an SAE. If the planned hospitalization should be prolonged due to an AE, an SAE would need to be documented.

bronchospasm requiring intensive treatment in an emergency room or at home, blood dyscrasias or convulsions that do not result in inpatient hospitalization, or the development of drug dependency or drug abuse.

#### **14.1.5. Unexpected Adverse Event or Unexpected Suspected Adverse Reaction**

An AE or suspected adverse reaction is considered “unexpected:”

- If it is not listed in the Investigator Brochure or is not listed at the specificity or severity that has been observed, or
- If an Investigator Brochure is not required or available, is not consistent with the risk information described in the general investigational plan or elsewhere in the current application, as amended.

For example, under this definition, hepatic necrosis would be unexpected (by virtue of greater severity) if the Investigator Brochure referred only to elevated hepatic enzymes or hepatitis. Similarly, cerebral thromboembolism and cerebral vasculitis would be unexpected (by virtue of greater specificity) if the Investigator Brochure listed only cerebral vascular accidents.

[figure not shown]
“Unexpected,” as used in this definition, also refers to AEs or suspected adverse reactions that are mentioned in the Investigator Brochure as occurring with a class of drugs or as anticipated from the pharmacological properties of the drug, but are not specifically mentioned as occurring with the particular drug under investigation.

### **14.2. Adverse Event Classification**

#### **14.2.1. Treatment-Emergent Adverse Events**

An AE is defined as treatment-emergent if it occurs at or after the first dose of study treatment and through 2 weeks after the last dose of study treatment. This also includes AEs which are observed before the first dose of study treatment and increase in severity after the first dose through 2 weeks after the last dose of study treatment.

Note: 2 weeks after the last dose of study treatment was selected because it is expected to be longer than 5 times the terminal half-life of ND-L02-s0201.

#### **14.2.4. Respiratory Adverse Events**

It is recognized that exacerbations of IPF occur and that they may be preceded by indolent symptoms. These indolent symptoms should be recorded per the site’s customary practices for reporting AE. When a subject’s status progresses to include sufficient respiratory deterioration, imaging findings, histopathology, and/or clinical interventions consistent with exacerbation of IPF, AE reporting should convert to this term as long as it is the same event. If the Investigator

determines that there is a relationship between the AE (eg, upper respiratory tract infection) and the exacerbation, the former term should be modified to indicate the relationship (eg, upper respiratory tract infection preceding IPF exacerbation or upper respiratory tract infection-related to IPF exacerbation). If the time-relationship is unclear, separate AEs are appropriate and IPF exacerbation should be captured as a new event.

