#### **14.2.5. Acute Exacerbation of IPF**

Idiopathic pulmonary fibrosis exacerbation is defined as an unexplained worsening of dyspnea, evidence of hypoxemia as defined by worsened or severely impaired gas exchange, new radiographic alveolar infiltrates, and an absence of an alternative explanation such as infection, pulmonary embolism, pneumothorax, or heart failure (Raghu et al, 2011).

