### **14.5. Documentation of Adverse Events by Investigator**

Subjects will be evaluated and questioned generally to identify AEs during the course of the study. Adverse event collection will begin 24 hours before Visit 1a. Adverse events that occur up to and including 12 weeks after administration of the last dose of study treatment, including ET, must be reported.

All AEs spontaneously reported by the subject and/or in response to an open question from study personnel or revealed by observation, physical examination, or other diagnostic procedures will be recorded on the Adverse Event Form for that visit. Any clinically relevant deterioration in laboratory assessments, intercurrent illness, or other clinical findings is considered an AE and must be recorded on the Adverse Event Form. In addition, an abnormal test finding will be classified as an AE if one or more of the following criteria are met:

- The test finding is accompanied by clinical symptoms.
- The test finding necessitates additional diagnostic evaluation(s) or medical/surgical intervention; including significant additional concomitant drug treatment or other therapy. Note: simply repeating a test finding, in the absence of any of the other listed criteria, does not constitute an AE.
- The test finding leads to a change in study treatment dosing or discontinuation of subject participation in the clinical research study.
- The test finding is considered an AE by the Investigator.

Wherever possible, a specific disease or syndrome rather than individual associated signs and symptoms should be identified. However, if an observed or reported sign or symptom is not considered a component of a specific disease or syndrome by the Investigator, it should be recorded as a separate AE. Laboratory data will be collected as stipulated in this protocol. Clinical syndromes associated with laboratory abnormalities will be recorded as appropriate (eg, diabetes mellitus rather than hyperglycemia).

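### Protocol Sections 14.2.4 and 14.2.5 set different tests for IPF exacerbation, and the SAP's tested exacerbation endpoints inherit whichever one the site applied

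*Protocol*

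**What the plan says.** Protocol Section 14.2.4 covers respiratory AEs that may develop into an exacerbation. On the early phase it says: "These indolent symptoms should be recorded per the site’s customary practices for reporting AE". Once the subject's status includes "sufficient respiratory deterioration, imaging findings, histopathology, and/or clinical interventions consistent with exacerbation of IPF", reporting is to convert to the exacerbation term, provided it is the same event. If the investigator sees a relationship between another AE and the exacerbation, the other AE's term is modified to show it; the examples are "upper respiratory tract infection preceding IPF exacerbation or upper respiratory tract infection-related to IPF exacerbation". If the timing is unclear, separate AEs are recorded and the exacerbation is entered as a new event.

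Section 14.2.5 defines the exacerbation itself: dyspnea that has worsened without explanation, hypoxemia, new infiltrates on imaging, "and an absence of an alternative explanation such as infection, pulmonary embolism, pneumothorax, or heart failure". Protocol Section 13.1.2.1 and SAP Section 3.2 repeat that definition for the secondary endpoint.

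Section 14.5 is the general recording rule. "All AEs spontaneously reported by the subject and/or in response to an open question from study personnel or revealed by observation", or found by examination or other diagnostic procedures, go on the AE form for the visit. It also prefers a disease or syndrome to its separate signs and symptoms where one can be identified.

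SAP Section 7.5.2.4 identifies the exacerbation as determined by the investigator, through the AE form and a preferred term of idiopathic pulmonary fibrosis.

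**The concern.** Two adjacent sections give the investigator different tests for the same AE term. Section 14.2.4 joins its findings with *and/or*, leaves *sufficient* undefined, and lets an exacerbation stand beside an infection related to it. Section 14.2.5 is conjunctive and rules the event out when infection explains it. Section 14.2.4 does not refer to 14.2.5.

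The label matters because it is the endpoint. The SAP runs a stratified log-rank test and a Cox model on time to first exacerbation or death, and a chi-squared test on the exacerbation rate. Acute exacerbation is also an AE of special interest (SAP Section 3.4.6). The visible text describes no adjudication and no check of the entry against 14.2.5, so an inconsistency at the site passes into the analysis.

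The secondary issue is the deference to site custom for early symptoms. TEAE incidence is a primary endpoint ("Incidence of TEAEs and treatment-emergent SAEs"), respiratory AEs are also of special interest, and the trial is spread thinly: "The study will include approximately 35-40 sites and will enroll approximately 3 to 5 subjects per site".

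**Working it through.** The documents give no exacerbation rate, respiratory AE rate or effect size, so there is no stated result to reproduce. The main check is a comparison of the text.

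**1. The two tests side by side**

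- *How findings combine.* 14.2.4: a list joined by *and/or*. 14.2.5: all elements together.
- *Infection.* 14.2.4: the exacerbation term can stand while an infection is recorded as preceding it or related to it. 14.2.5: an infection that explains the worsening excludes the event.
- *Endpoint text.* Protocol 13.1.2.1 and SAP 3.2 follow 14.2.5.
- *Endpoint data.* SAP 7.5.2.4 follows the AE entry, which a site may have made under 14.2.4.

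**2. One case traced through.** A subject has an upper respiratory infection, then worsening dyspnea, hypoxemia and new infiltrates, which the investigator attributes to the infection. Under 14.2.4 the site can enter an IPF exacerbation and modify the infection term to show the link. If the entry codes to the SAP's preferred term, the subject has an event in both tested analyses. Under 14.2.5 the infection is the alternative explanation: no exacerbation is entered and the subject has no event, unless death follows and counts in the composite. The clinical course is the same; the endpoint value differs.

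**3. Onset date.** Conversion applies when it is the same event, but 14.2.4 does not say whether the start date is that of the early symptoms or of the deterioration. A time-to-event analysis needs one of them.

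**4. Size of one reclassified subject**

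- Arms: 3 × 40 = 120, which agrees with the planned total.
- One subject as a share of an arm: 1/40 = 2.5 percentage points.
- Relative to the arm's exacerbation count, under an assumption that is not in the documents of 2 to 5 such subjects per arm: 1/5 = 20% to 1/2 = 50%.

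**5. Recording of early symptoms.** Subjects per site: 120/40 = 3.0 to 120/35 = 3.4. Per arm at a site: 40/40 = 1.0 to 40/35 = 1.1. SAP Section 2.2 stratifies by standard of care and does not name site, so stratification does not balance recording habits across arms. Chance imbalance is noise, not a systematic shift. The share of symptoms that custom would leave unrecorded is not in the documents, so no effect on TEAE incidence can be calculated.

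**The case against.** The best defense is that the sections can be read together: 14.2.4 says when to change a term and 14.2.5 says what the term means. The findings in 14.2.4 must be sufficient and consistent with exacerbation of IPF, which could import the next section's definition. An infection that merely precedes an exacerbation need not be its explanation. This narrows the conflict but does not remove it. The example of an infection related to the exacerbation still sits against the exclusion in 14.2.5, and nothing visible tells a site which section governs.

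Three stronger readings are tempting, and the documents do not support them.

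- A reader might infer that infection is itself a trigger for the exacerbation term. It is not; 14.2.4 only says how to word the infection's own term when a link is seen.
- A reader might infer that a site could leave new cough or dyspnea off the AE form and still comply. Section 14.2.4 says the symptoms should be recorded and Section 14.5 continues to apply. What is left to custom is how they are recorded. Monitors also compare eCRF entries with source and report omissions (Section 16.2.3).
- A reader might infer that site custom shrinks the active-placebo difference in respiratory TEAEs by a calculable amount. The clause covers only symptoms that may precede an exacerbation, and a subject who goes on to exacerbate is still recorded under the converted term. In the any-TEAE summary subjects count once, so a missed symptom matters there only if the subject has no other TEAE. SAP Section 7.6.2 plans no statistical comparison of AEs between arms.

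Investigators are blinded and allocation is randomized, so neither issue by itself favors an arm. Sections 14.2.2, 14.2.3 and 14.2.6 are not legible in the public text; related rules there cannot be seen and are not counted as missing.

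**Conclusion.** The conflict over the exacerbation term holds and should be corrected. The endpoint is defined by the strict test but populated from an entry that a site may make under the looser one, and it feeds two analyses that are formally tested. The effect is misclassification of infection-linked worsening, and of cases meeting only some elements of the definition, plus an unspecified event date after conversion. Each reclassified subject is 2.5 points of a 40-subject arm. The relative figure of 20% to 50% rests on the assumed 2 to 5 events, and the number of subjects affected is unknown.

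The deference to site custom is a lesser point: possible noise or under-counting in all arms, of a size that cannot be derived. It does not show that the primary endpoint is biased.

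**What to change.** In protocol Section 14.2.4:

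1. Allow conversion to the IPF exacerbation term only when the Section 14.2.5 definition is met.
2. When the investigator judges that an infection or another cause explains the worsening, keep that cause as the AE term and do not count the event as IPF exacerbation. Align the worked examples with this.
3. State which onset date applies after a term is converted, so that the time-to-event analysis in SAP Section 7.5.2.4 has one rule.
4. Replace the reference to site custom with a reference to Section 14.5, including its preference for a syndrome over its separate symptoms, so that one episode is not split into several AEs.

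The cost is a few lines of protocol text and a short memo to sites. The downside is slightly fewer events labelled IPF exacerbation. These changes concern recording and classification only, not the care of subjects.

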#### **14.2.5. Acute Exacerbation of IPF**

Idiopathic pulmonary fibrosis exacerbation is defined as an unexplained worsening of dyspnea, evidence of hypoxemia as defined by worsened or severely impaired gas exchange, new radiographic alveolar infiltrates, and an absence of an alternative explanation such as infection, pulmonary embolism, pneumothorax, or heart failure (Raghu et al, 2011).

#### **14.2.7. Relationship to Study Treatment, Premedication, and Standard of Care**

Relationship to study treatment, premedication, and standard of care will be assessed. Hereafter referred to as drug in this section.

The Investigator's assessment of causality must be provided for all AEs (serious and nonserious). An Investigator's causality assessment is the determination of whether there exists a reasonable possibility that the drug caused or contributed to an AE. The possibility of a causal relationship means that there are facts, ie, evidence, or arguments to suggest a causal relationship. Adverse events with a relationship of "none" are considered not related to drug. All other AE relationships (unlikely, possible, probable, and definite) are considered related to drug.

Clinical judgement should be used to determine the relationship of drug to the AE. The Investigator should consider, for example, all relevant and/or alternative causes, including pattern of the reaction, temporal relationship, de-challenge, re-challenge, underlying disease(s), concomitant therapy(ies), concomitant illness(es), risk factor(s), and medical history.

None: No relationship between the experience and the administration of drug; related to other etiologies such as concomitant medications or subject's clinical state.

Unlikely: The current state of knowledge indicates that a relationship is unlikely. However, as a causal relationship to the drug cannot be ruled out, the causal relationship will be classified as related to drug.

Possible: A reaction that follows a plausible temporal sequence from administration of the drug and follows a known response pattern to the suspected drug. The reaction might have been produced by the subject's clinical state or other modes of therapy administered to the subject, but this is not known for sure.

Probable: A reaction that follows a plausible temporal sequence from administration of the drug and follows a known response pattern to the suspected drug. The reaction cannot be reasonably explained by the known characteristics of the subject's clinical state or other modes of therapy administered to the subject.

Definite: A reaction that follows a plausible temporal sequence from administration of the drug and follows a known response pattern to the suspected drug and can be confirmed with a positive re-challenge test or supporting laboratory data.

Note: AEs that occur after administration of premedication (if applicable) but before the administration of study treatment should not be reported as related to study treatment.

Refer to the country-specific package insert of Summary or Product Characteristics for the risks and side effects associated with pirfenidone, nintedanib, and premedication (if applicable).

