#### 12.2.4. Visits 5, 7, 9, 11, and 13 (Days 43, 71, 99, 127, 155) All Subjects

Each of Visits 5, 7, 9, 11, and 13 will be conducted  $14 \pm 7$  days after the previous dose of study treatment. The following study procedures will be performed at these visits **before** the study treatment infusion:

- Record AEs and the status of previously unresolved AEs.
- Record concomitant medications.
- [REDACTED]
- Administer premedications, if applicable (see Section 18.5).
- Measure vital signs (systolic and diastolic blood pressure, heart rate, respiration rate, and oral temperature) and SpO2 once before the study treatment infusion (if premedication is administered, vital signs should be measured after premedication).
- Administer assigned study treatment.

The following study procedures will be performed at these visits **during** the study treatment infusion:

- Measure vital signs (systolic and diastolic blood pressure, heart rate, respiration rate, and oral temperature) and SpO2 midinfusion  $\pm$  5 minutes (if infusion is administered at a modified rate [REDACTED] the timing should correspond to the middle of the modified infusion duration).

The following study procedures will be performed at these visits **after** the study treatment infusion:

- Measure vital signs (systolic and diastolic blood pressure, heart rate, respiration rate, and oral temperature) and SpO2 within 15 minutes after the end of the study treatment infusion.

[REDACTED]

[REDACTED]

Refer to Section 18.6 for guidance on clinical trial conduct relating to COVID-19.

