## 18.5. Appendix E: Premedication

Subjects may be premedicated to mitigate the risk of infusion-related reactions at the discretion of the Investigator.

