### 3.4.6 Adverse Events (AEs)

All AEs recorded on the eCRF will be coded using the latest version of MedDRA dictionary, per the Data Management Plan, throughout the study and classified as either pre-treatment AEs or TEAEs as follows:

- Pre-treatment AEs are events that started prior to the first dose of any study treatment, including pre-medication.
- TEAEs are events that occur on or after the first dose of any study treatment including pre-medication through two weeks after the last dose of study treatment or adverse events which start before the first dose of study treatment, but increase in severity after the first dose through two weeks after the last dose of study treatment.

Assessment of AE severity will be based on the National Cancer Institute (NCI) Common Terminology Criteria for Adverse Events version 5.0 (CTCAE v5.0). The severity of all AEs is recorded as mild (Grade 1), moderate (Grade 2), severe (Grade 3), life threatening consequences (Grade 4), or death (Grade 5), per CTCAE grading. If severity is missing for a TEAE, it will be considered severe only in the overall category in the summary tables.

The relationship between an AE and study treatment is assessed as definite, probable, possible, unlikely, or none. A drug-related AE is an AE considered by the investigator as definitely, probably, possibly, or unlikely related to study treatment. If the relationship is unknown or missing, it is also considered as related to study treatment.

AEs of special interest (AEOI) include [REDACTED] respiratory adverse events, and acute exacerbation of idiopathic pulmonary fibrosis.

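### The causality note on events between premedication and infusion has no first-dose limit, and the protocol and SAP start the TEAE window at different points

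*Protocol*

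**What the plan says.** **Causality.** Protocol 14.2.7 wants an investigator rating for every AE and says that "Clinical judgement should be used to determine the relationship of drug to the AE". Of the five ratings, only *none* means not related: "All other AE relationships (unlikely, possible, probable, and definite) are considered related to drug". The section closes with a note that "AEs that occur after administration of premedication (if applicable) but before the administration of study treatment should not be reported as related to study treatment". The note names no visit, day or dose number.

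**Premedication.** Protocol 18.5 states that "Subjects may be premedicated to mitigate the risk of infusion-related reactions at the discretion of the Investigator". Sections 12.2.1 to 12.2.5 list optional premedication ahead of the infusion at every dosing visit, Visits 2 to 13.

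**TEAE start.** Protocol 14.2.1: "An AE is defined as treatment-emergent if it occurs at or after the first dose of study treatment". SAP 3.4.6: "TEAEs are events that occur on or after the first dose of any study treatment including pre-medication". SAP 5.5, when it defines evaluable subjects, expressly leaves premedication out of study treatment.

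**The concern.** The note is sound before the first infusion, because no study drug or placebo has yet been given. From Visit 3 on that reasoning fails. The subject has already had one or more infusions, and an investigator who thinks an earlier infusion may have contributed has no compliant way to say so. Clock time replaces judgement for those events. At stake are the SAP 7.6.2 tables of drug-related TEAEs and drug-related serious TEAEs, and the causality rating sent with an SAE report.

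The TEAE start is a separate matter with a different consequence. It decides which events enter the primary safety endpoint, and the two documents give different answers for one short interval on Day 1.

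**Working it through.** **1. How many windows the note covers.** Dosing days in the schedule (Visits 2 to 13) are 1, 15, 29, 43, 57, 71, 85, 99, 113, 127, 141 and 155. That is 12, matching the 12 doses stated in protocol 7.1. Only the first has no earlier infusion, so 12 − 1 = 11 of the 12 possible premedication-to-infusion windows (11/12 = 92%) follow prior exposure. This counts visits, not events or subjects.

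**2. What the note leaves available.** Four of the five ratings count as related, so the only rating that complies is *none*. Leaving the rating blank is no way out: 14.2.7 requires one, and SAP 3.4.6 counts a missing relationship as related. The note does not restrict the separate rating against premedication.

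**3. Whether an earlier dose can be dismissed.** Protocol 14.2.1 says that 2 weeks is expected to exceed 5 terminal half-lives. The half-life is then below 14/5 = 2.8 days. Assuming first-order elimination, the fraction of the previous dose remaining is at most 2^(−gap/2.8):

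| Gap since previous infusion | Upper bound on fraction remaining |
|---|---|
| 7 days (minimum between doses) | 2^(−2.5) = 17.7% |
| 10 days (earliest Visit 3) | 2^(−3.57) = 8.4% |
| 14 days (nominal) | 2^(−5) = 3.1% |

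Most drug should be gone at the nominal gap, but the protocol's own figures do not make an effect of the earlier dose impossible. The bound concerns drug remaining, not how long an effect lasts.

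**4. The definitions side by side.**

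| Onset of AE | Protocol 14.2.1 | SAP 3.4.6 | Rating against study treatment |
|---|---|---|---|
| Day 1, before premedication | Not a TEAE unless it worsens | Pre-treatment unless it worsens | Note does not apply |
| Day 1, premedication to infusion | Not a TEAE unless it worsens | TEAE | *None*, appropriately |
| Visits 3–13, before that day's premedication | TEAE | TEAE | Investigator's judgement |
| Visits 3–13, premedication to infusion | TEAE | TEAE | *None*, whatever the judgement |

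The fourth row is the causality problem and the second row is the TEAE mismatch. The rows do not overlap.

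**5. Which outputs move.** The primary endpoints (protocol 13.1.1, SAP 3.1) count TEAEs, serious TEAEs and discontinuations due to TEAEs without regard to relatedness, so the fourth row does not touch them. It affects the relatedness summaries in SAP 7.6.2. The second row does reach the primary endpoints. Neither row can be turned into an event count: the readable text gives no premedication rate, no lead time and no AE rate.

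**The case against.** A first-dose-only intent is plausible. It would make the note agree with the rest of 14.2.7, and qualifying text could sit in redacted parts of Sections 14.2 or 18.5. That stands as a caution. But the limit is not written, and the note points to no other section for one.

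A reader might infer several stronger claims that the documents do not support:

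- *All events after earlier infusions are forced to not related.* No. Events that start before that day's premedication, and all events in subjects not premedicated, stay under ordinary judgement.
- *Pre-infusion vital signs will feed many events into the window.* They are taken after premedication, but a reading can reveal something that began earlier, AE recording is listed ahead of premedication, and protocol 14.5 sets criteria before a test finding becomes an AE.
- *Serious unexpected reactions will escape expedited reporting.* Protocol 14.6.1 sends every SAE to the sponsor within 24 hours regardless of relatedness, in enough detail for an independent view on causality, and the DMC reviews all available AEs. These are real, though partial, safeguards. They do not correct the investigator's recorded rating.
- *Every affected rating is wrong.* For an event truly unrelated to earlier dosing, *none* is correct.
- *The SAP's TEAE start is a mistake.* It agrees with the SAP's general baseline rule (7.1), which also precedes premedication, and with the planned table of premedication-related TEAEs (7.6.2). It may be deliberate. The investigator is blinded and no infusion has been given, so the extra Day 1 events should not systematically favour an arm.

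**Conclusion.** The note is wrong as written for Visits 3 to 13. It requires *none* where the same section requires judgement and where 14.2.1 classes the event as treatment-emergent. It can only lower the drug-related TEAE and SAE counts and the investigator's SAE ratings. The effect is confined to premedicated subjects and to AEs with onset in a short window, so it is probably small, and it cannot be quantified from the documents. SAP 7.6.2 plans no statistical comparison of AEs, so no test result depends on it.

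The TEAE start differs between protocol and SAP for Day 1 events between premedication and the first infusion, and this reaches the primary endpoint. It is a discrepancy to reconcile or declare, not a demonstrated error. The readable part of SAP Section 8 does not list it as a change, but that section is partly redacted, so non-declaration cannot be established.

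Both conclusions rest on the literal wording and on no limit being stated in redacted text.

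**What to change.** **Protocol 14.2.7.** Restrict the note to AEs with onset after premedication and before the *first* infusion of study treatment (Visit 2). Add that at later visits an AE between premedication and infusion is assessed against earlier infusions and against the premedication in the usual way.

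**TEAE start.** Choose one:

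- Align SAP 3.4.6 with protocol 14.2.1 and tabulate Day 1 events between premedication and the first infusion separately, so that they are not lost from the safety report.
- Keep the SAP definition and declare it in SAP Section 8 as a change from the protocol.

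In either case, use the term study treatment in one sense throughout SAP 3.4.6 and 5.5.

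**Cost.** A sentence or two in each document. The protocol change would generally need ethics approval under 16.8 and a reminder to sites. Applying either rule needs AE onset times and premedication times on dosing days. Infusion start times are already recorded (10.4) and premedication is already reported on the eCRF (18.5.3); whether clock times are captured for AEs and premedication should be checked.
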